		Visit					

Page 7 of 17 IRB19-0017 Version 2; date: 4/11/19

	Screening	1	2	3	4	5	6			
Consent Forms:	Х									
Medical Procedures on Child										
Blood draw		Х					Х			
Heart rate		х	Х	Х	Х	Х	Х			
Blood pressure		х	Х	Х	Х	Х	Х			
		Pare	nt Reports	on Child						
Aberrant Child Checklist	Х	Х	Х	Х	Х	Х	Х			
Social responsiveness Scale	Х	Х	Х	х	х	х	х			
Clinical Global Impression Scale	Х	Х	Х	Х	Х	Х	Х			
PRAS ASD	Х						Х			
Vineland-3	Х						Х			
Side effects checklist		Х	Х	Х	Х	Х	Х			

Subject Recruitment

All potential subjects for this study will be recruited through the Child and Adolescent Psychiatry Department Neurodevelopmental clinic and by Neuropsychological referral.

Subjects:

Inclusion criteria:

- 1) Boys and girls ages 4-17;
- 2) Current diagnosis of Autism Spectrum Disorder as determined by criteria in DSM-5
- 3) Parents of Children ages 4-17 with a current diagnosis of Autism Spectrum Disorder as determined by criteria in DSM-5

Exclusion criteria:

- 1) Unstable medical illness or clinically significant abnormalities on physical examination;
- 2) History of seizures;
- 3) History of Hematological disorders;
- 4) Myocardial infarction within 6 months;
- 5) Current pregnancy or lactation, or inadequate contraception in girls of childbearing potential;
- 6) Current or recent (past 3 months) DSM-5 substance abuse or dependence;
- 7) Illegal substance use within 2 weeks of study initiation;
- 8) Previous treatment with Glutathione;
- 9) Current treatment with N-acetylcysteine, milk thistle, Vitamin C, Vitamin B, Grape Seed Extract, Amino Acids, or Zinc (known to interfere with Glutathione level)
- 11) Current treatment with Dextromethorphan, D-cycloserine, Amantadine, Memantine, Lamotrigine or Riluzole (known to have glutamatergic properties)
- 12) Asthma (given this is rare, but possible worsening of asthma symptoms due to Glutathione)

Assessments:

Existing Data

Before beginning Glutathione, all subjects will have a psychiatric, medical, and family history evaluation completed as part of their standard clinical care.

New Data Collection

At the screening visit, all subjects will receive a physical examination. For all subjects, at the initial visit, blood work will be obtained for a baseline Glutathione level. Glutathione level will also be obtained at study completion. Total amount of blood to be obtained will be 4 teaspoons. PI will obtain neuropsychological evaluations report if it is available.

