24 male and female outpatients aged 4-17 with a primary diagnosis of Autism Spectrum Disorder.

-Note on sample size: The sample size is low due to this being a pilot feasibility study and the primary aim of the study is not to examine the effectiveness of oral glutathione as a treatment but rather examine the functionality of providing oral glutathione on the blood level, the data will likely be used for future studies on treatment or grant applications. There also is no external sponsor, therefore internal funding limits the number of subjects.

Participant Exclusion:

For this study, children under the age of 4 and adults over the age of 17 will be excluded. The rationale for this is that the study population of interest are pediatric subjects in the children and adolescent age ranges.

Data Analysis:

Primary analyses will be intent-to-treat with last observation carried forward. Changes in the blood level of glutathione will be the primary outcome measure. For both primary and secondary measures, random regression analysis will be conducted using the MIXREG program

Demographic and baseline visit characteristics of the Glutathione treatment patients will be documented. Primary and secondary measures will be examined using analysis of variance modeling analyses (SPSS). The difference in the overall level of posttreatment values, the main effect for treatment, will be the test of primary interest. Analyses will be performed on all available data by the use of an intention-to-treat population (last observation carried forward). All patients who return for at least 1 follow-up visit will be included in the intention-to-treat population. Effect sizes will also calculated using the Cohen effect size index d. A d of 0.2 is considered a small effect size, 0.5 is medium, and 0.8 is large. Partial eta squared (η 2), which is the proportion of the effect + error variance that is attributable to the effect, will be calculated. Interpretation of η 2 is that greater than 0.2 is a large effect size, greater than 0.1 is a medium effect size, and greater than 0.05 is a small effect size.

The CGI severity scale will be used to assess clinically significant change after treatment. For someone to have a clinically significant change, her or his final CGI severity score had to be less than the cutoff score, and her or his change from baseline had to be greater than the reliable change index

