The study will end once 24 subjects have been recruited and have completed the study visits. At this point, the data analysis will then begin.

Potential Risks and Benefits:

The study supplement Glutathione may help to decrease problem behaviors and irritability that can be seen in children with Autism Spectrum Disorder. It is also postulated that the information learned from this study will benefit other individuals and children and adolescents with problem behaviors related to Autism Spectrum Disorder in the future.

Page 11 of 17 IRB19-0017 Version 2; date: 4/11/19 Most supplements can cause side effects, but are typically safe. Side effects are usually reversible when the supplement is stopped. The most common side effects associated with Glutathione include; upset stomach, diarrhea, dizziness, dry mouth or headaches and sometimes, but rarely a skin rash, skin flushing or respiratory distress can be seen. As such, patients with asthma or allergies that have resulted in respiratory distress in the past will not be included in this study to ensure safety.

Safety Assessments:

Safety assessments (sitting blood pressure, heart rate, adverse effects, and concomitant medications) will be documented at each visit. In terms of vital signs, those subjects with abnormal blood pressures will be assessed for symptoms of hypo- or hypertension. Asymptomatic subjects will be evaluated each visit for changes in vital signs. In the case of hypertensive emergencies (BP greater than 210/120), appropriate referral to the emergency room will be made. In the case of hypotension (BP less than 90/60), participants will be evaluated for symptoms of hypotension and if symptomatic, appropriate interventions will be made. Subjects who endorse suicidal thoughts at any time during the study will be removed from the study and appropriate clinical intervention (e.g. hospitalization) will be arranged.

At the initial visit, blood work will be obtained for a baseline Glutathione level and an end point Glutathione level will also be obtained at study completion. Assessment of side effects will be done at each visit. Participants will be advised concerning the risk of allergic reactions to Glutathione: skin rash, skin flushing, drop in blood pressure, irregular heartbeat, and respiratory distress. Although is it extremely rare but participants will be advised to visit an emergency room for symptoms suggestive of anaphylactoid reactions.

Adverse Event Reporting:

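### Carrying the last value forward records zero glutathione change for every analysed patient without the end draw, which shrinks the primary estimate if those patients resemble completers

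*Combined protocol and SAP*

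**What the plan says.** Four statements in the combined protocol and SAP combine to produce the problem.

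- **Outcome and missing-data rule (Data Analysis).** Change in blood glutathione is the primary outcome, and "Primary analyses will be intent-to-treat with last observation carried forward". The same section repeats the carry-forward rule when it describes the analysis population.
- **Measurement times (Assessments, New Data Collection).** At the initial visit, "blood work will be obtained for a baseline Glutathione level. Glutathione level will also be obtained at study completion". Safety Assessments agrees: "an end point Glutathione level will also be obtained at study completion". The schedule table marks blood only in the Visit 1 column and the last column. No intermediate draw and no draw at early withdrawal is described.
- **Who is analysed (Data Analysis).** "All patients who return for at least 1 follow-up visit will be included in the intention-to-treat population". A second glutathione value is not required.
- **What is reported (Data Analysis).** "Effect sizes will also calculated using the Cohen effect size index d", and partial eta squared is also planned.

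The section names a second method as well: "For both primary and secondary measures, random regression analysis will be conducted using the MIXREG program". It does not say whether that model is fitted to observed values or to values filled in by carry-forward.

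**The concern.** Carry-forward is usually defended as using a patient's latest on-treatment value. With one pre-treatment and one end-of-study draw there is no on-treatment value to use. A patient who attends, say, two follow-up visits and then leaves is in the analysed set. That patient enters the primary result as a measured null response, although nothing was measured after treatment began.

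The note on sample size calls this a pilot and says that "the data will likely be used for future studies on treatment or grant applications". The estimated change and Cohen's d are therefore main products of the study. If they are pulled towards zero by however many end draws happen to be missing, later studies will be planned on a figure that mixes a biological effect with an attendance rate.

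For the Aberrant Behavior Checklist, the Social Responsiveness Scale and the CGI, which are collected at every visit, the zero-change problem is less acute. The unclear relation between carry-forward and MIXREG matters there too.

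**Working it through.** **Inputs from the protocol:** 24 subjects in a single arm, two glutathione draws, carry-forward, and an analysed set defined by one follow-up visit. There is no power calculation, expected effect, SD or dropout rate, so there is no planned figure to reproduce.

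**Assumptions:** 2, 5 or 7 of 24 analysed patients have a baseline value but no end draw; their true change has the same distribution as that of completers; effects are in units of the SD of change (s = 1).

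**Step 1, the imputed value.** Change = carried-forward value − baseline = baseline − baseline = 0.

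**Step 2, mean change.** Let m be the share without an end draw and δ the true mean change. The expected mean is (1 − m)δ. The retained share is 22/24 = 0.917, 19/24 = 0.792 or 17/24 = 0.708, a loss of 8%, 21% or 29%.

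**Step 3, Cohen's d.** The variance of change becomes (1 − m)s² + m(1 − m)δ². With the change-score SD as standardiser and d = δ/s:

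d under carry-forward = d√(1 − m) / √(1 + m d²).

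For d = 0.8 and m = 5/24: 0.8 × 0.890 / √(1 + 0.208 × 0.64) = 0.712 / 1.065 = 0.669. The plan does not name a standardiser. With the baseline SD the result is (1 − m)d, here 0.792 × 0.8 = 0.633. On a grid of missing shares, SD ratios and effects, d also shrank with the post-treatment SD and with the pooled SD.

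**Step 4, behaviour at n = 24.** 200,000 simulated trials per setting, with changes drawn from N(d, 1) and the missing ones set to 0, compared with a paired analysis of observed changes:

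| End draws missing | Mean kept | d = 0.8 by formula | d = 0.8, average, carry-forward | d = 0.8, average, observed pairs | 95% CI coverage at 0.6 SD | 95% CI coverage at 1.0 SD |
|---|---|---|---|---|---|---|
| 2 | 92% | 0.746 | 0.768 | 0.831 | 0.95 | 0.94 |
| 5 | 79% | 0.669 | 0.682 | 0.835 | 0.90 | 0.84 |
| 7 | 71% | 0.618 | 0.628 | 0.839 | 0.84 | 0.70 |

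The coverage columns are for carry-forward; observed pairs gave 0.95. Both average d values lie above their population values because sample d is biased upward in small samples. The coverage loss comes mainly from the shifted centre: with 5 missing at 0.6 SD, the reported SE (0.186) is not smaller than the sampling SD of the mean (0.182). Partial eta squared with 5 missing at 0.8 SD averages 0.32, against 0.41 from observed pairs.

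**Step 5, the test against zero** (two-sided 5% assumed, 5 missing). Type I error is 0.049. Power at 0.6 SD is 0.692, against 0.695 for observed pairs.

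**Step 6, other readings.**
- *Timing of leaving.* Patients who leave before any follow-up visit are excluded, not set to zero. If 5 of 24 leave and j of them had no follow-up visit, the retained share is 19/(24 − j). It runs from 79% (j = 0) to 100% (j = 5).
- *Replacement.* If leavers are replaced until 24 complete, 5 zeros among 29 give 5/29 = 17% attenuation; for 2 and 7 leavers it is 2/26 = 8% and 7/31 = 23%.
- *Opposite assumption.* If patients without an end draw truly had no change, carry-forward is right. Observed pairs then overstate the all-patient mean by 24/19 − 1 = 26% with 5 missing.

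**The case against.** The strongest reply is that the primary question, whether the level rises, is answered almost equally well either way. Step 5 confirms this, and it limits the concern to estimation.

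Second, the size depends on a dropout rate that the protocol does not give. The Data Analysis section also says: "The study will end once 24 subjects have been recruited and have completed the study visits". On one reading that means 24 end draws. If no analysed patient lacks the end draw, nothing is lost. Yet the plan still provides for carry-forward, and patients who left after a follow-up visit remain in its analysed set.

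Third, no confidence interval is promised, so the coverage figures describe a natural output and not a planned one. That is fair. The planned outputs, d and partial eta squared, shrink as well.

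Fourth, attenuation is not always a worse estimate. At a true d of 0.8 with 5 missing, the root-mean-square error of d is about 0.23 under carry-forward and 0.29 for observed pairs. This is accidental shrinkage, by an amount set by attendance. For the mean change it already reverses at 0.8 SD (0.246 against 0.229).

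Fifth, patients who leave for poor tolerability may have had less exposure, so resembling completers may be the less plausible case. This stands as a caution, and it is why zero change should be kept as a sensitivity analysis.

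Sixth, MIXREG fitted to observed glutathione values would contain no zeros, and a convention of never carrying a baseline forward would avoid them. The plan states neither, and the second would drop patients whom it says it includes.

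**Conclusion.** The concern holds. The mechanism follows from the text alone: two draws, carry-forward on the primary outcome, and an analysed set that does not require the second draw. Its size is conditional. Under the assumption that patients without an end draw resemble completers, 5 missing of 24 cost about a fifth of the mean change and take the average d from about 0.83 to 0.68 at a true 0.8. With 2 missing the loss of mean change is 8%. With none missing there is no loss, and if those patients truly did not change, the zeros are correct. The significance test is sound in all the cases examined. This should be fixed because it biases the estimate that the pilot exists to supply; it does not invalidate the trial.

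**What to change.** 1. Remove carry-forward from the primary glutathione analysis. Define the primary analysis as the paired change in subjects who have both the baseline and the study-completion draw.
2. Report how many analysed patients lack the end draw, with reasons.
3. Present zero-change imputation as a labelled sensitivity analysis, so that the assumption is visible.
4. For the Aberrant Behavior Checklist, the Social Responsiveness Scale and the CGI, state that MIXREG is fitted to all observed visits without filled-in values. Apply the same statement to any MIXREG or SPSS model run on glutathione.
5. Optional, where feasible: take the planned second draw when a patient withdraws early. Record time on treatment and time since the last dose, and do not pool it unmarked with the 12-week draws.

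Items 1 to 4 are wording changes. Their price is a primary analysis that may have fewer than 24 subjects and that assumes missing end draws are unrelated to the change; item 3 probes that assumption. Item 5 alters a study procedure and needs IRB approval first.

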The following instruments will be completed at each visit throughout the study: 1) Aberrant Behavior Checklist [ABC], a 58-item parent report subjective scale used for assessing problem behavior in subjects with intellectual and developmental disabilities; 2) Social Responsiveness Scale [SRS], a 65-item parent report questionnaire designed to use with children ages 4-17, providing age- and gender-referenced ranges and assessing social deficits pertaining to autism and

Page 9 of 17 IRB19-0017 Version 2; date: 4/11/19 other domains; and 3) the Clinical Global Impression scale [CGI]; 7 point scale to measure symptom severity. Also, readings of patients' heart rates and blood pressures will be obtained; and assessment of side effects will be done at each visit.

Note on ABC and SRS:

The ABC is a standardized scale used for assessing problem behaviors in subjects with developmental and intellectual disabilities. The items are divided into five subscales: 1) Irritability; 2) Lethargy/Social Withdrawal; 3) Stereotypic Behavior; 4) Hyperactivity; and 5) Inappropriate Speech. High scores are indicative of severe behavioral symptoms. The ABC will be used to track the subjects' problem behaviors and difficulties over the course of the study. The severity of the subjects' problem behaviors must be assessed and examined its relationship with a baseline blood level of glutathione. In addition, by using this scale, we can observe the overall effect of oral Glutathione on problem behaviors, especially comparing the end results to the baseline.

The SRS is being used for the same purpose, although it is being used for secondary outcome measures. It is a parent report questionnaire designed for use with children aged 4-17 and provides age- and gender-referenced, as well as raw scores for the following domains: total score (reflecting severity of social deficits pertaining to autism); receptive, expressive, cognitive and motivational aspects of social behavior; and autistic preoccupations. High scores are also indicative of severe behavioral symptoms.

Note on additional measures:

Clinical Global Impression (CGI) (Severity) scale will be used by the clinician to assess overall severity of problem behaviors in Autism Spectrum Disorder subjects at baseline. This will be used as a secondary outcome measure over the course of the study and relates to Aim #1.

Study Population/Sample Size

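### Two unranked models are set for the same measures, and the one sentence naming a deciding test asks for a treatment effect that a single-arm trial cannot supply; the choice matters for the ABC, SRS and CGI, not for glutathione

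*Combined protocol and SAP*

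**What the plan says.** **Data Analysis, first paragraph.** The outcome is fixed: "Changes in the blood level of glutathione will be the primary outcome measure". The method follows: "For both primary and secondary measures, random regression analysis will be conducted using the MIXREG program". The random effects, and the way time enters the model, are not described.

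**Data Analysis, second paragraph.** A second method is given for the same measures: "Primary and secondary measures will be examined using analysis of variance modeling analyses (SPSS". The factors are not stated. Then comes the one sentence that ranks anything: "The difference in the overall level of posttreatment values, the main effect for treatment, will be the test of primary interest". Last observation carried forward is the rule for missing data.

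**Data Analysis, last paragraph on the CGI.** "The CGI severity scale will be used to assess clinically significant change after treatment", by a cutoff and a reliable change index whose values are not given.

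**Note on ABC and SRS.** The ABC is to show the overall effect on problem behaviour, "especially comparing the end results to the baseline". The SRS is said to serve the same purpose as a secondary outcome. Five ABC subscales are listed and none is singled out. The ABC itself is not labelled primary or secondary.

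**Timing.** Under New Data Collection, "at the initial visit, blood work will be obtained for a baseline Glutathione level"; under Safety Assessments, "an end point Glutathione level will also be obtained at study completion". That makes two draws per child. The Procedure section has the ABC, SRS and CGI completed at screening and at every visit.

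**Design.** There is one open-label arm of 24 children. No significance level, sidedness or multiplicity rule is given.

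**The concern.** When two models are assigned to one set of measures and neither is called primary or supportive, the team can follow the plan faithfully and still decide after seeing the data which result to report. The sentence that should settle this does not. A treatment main effect needs a comparison group. With one arm it would have to be redefined as a time effect, and the text does not say whether that means the average over all visits on treatment or the change from baseline to the end.

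What is at stake is the behaviour result. Project Goals hypothesises less irritability and fewer problem behaviours, and the note on sample size expects the data to feed later studies or grant applications. An effect size picked from several analyses would carry its optimism into those plans.

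**Working it through.** The plan's only relevant figure, N = 24, is justified by pilot status and funding. It has no calculation to reproduce.

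**1. Can the deciding test be carried out?** Arms: one. Levels of treatment: one. A main effect of a factor with one level has zero degrees of freedom, so the sentence cannot be executed as written.

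**2. Glutathione: do the models differ?** With two draws and complete pairs, all the usual models test the mean of (end − baseline). On one simulated set of 24 pairs:

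| Analysis | Result |
|---|---|
| Paired t | t = 2.673 (p = 0.0136) |
| Repeated-measures ANOVA | F = 7.143, the square of the paired t |
| Random intercept | t = 2.673 |
| Random intercept and slope | t = 2.673 |

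Two draws supply 3 variance-covariance elements (two variances and one covariance). Variance parameters needed:
- random intercept: 2, estimable;
- independent intercept and slope: 3, just identified;
- intercept and slope with a free covariance: 4, not identified. Residual variances of 0.05, 0.20, 0.35 and 0.45 all reproduced the same covariance matrix exactly.

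Even in the last case the test of mean change was unaffected.

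**3. ABC, SRS and CGI: do the tests differ?** The dosing schedule puts visits at Weeks 0, 2, 4, 8 and 12. Null simulations used n = 24, complete data and an assumed two-sided 5% for each test.

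| Setting | Chance of at least one p < 0.05 |
|---|---|
| End versus baseline alone, one score | 4.9% to 5.1% |
| Best of trend, average over visits, end versus baseline; one score, serially correlated errors | 7.7% to 9.1% |
| Best of trend, ANOVA over visits, end versus baseline; one score, 20,000 runs | 9.6% to 10.3% |
| Same three tests, five ABC subscales, 8,000 runs | 42% (between-subscale correlation 0) to 29% (0.7) |
| End versus baseline only, five ABC subscales | 23% to 15% |

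Reference values for three tests: 1 − 0.95³ = 14.3% if independent; upper bound 3 × 5% = 15%. Monte Carlo error at 10% with 20,000 runs is √(0.10 × 0.90 / 20,000) = 0.2 percentage points, so the spread in the one-score rows comes from the assumed correlations and the choice of tests.

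**4. Do they estimate the same thing?** Daily doses before the four post-baseline visits, from the dosing regimen, are 1000, 2000, 3000 and 3000 mg in the heavier group, and 1000, 2000, 2000 and 2000 mg in the lighter group. If effect were proportional to dose (an assumption), the visit average as a share of the full-dose change would be:
- heavier: (1000 + 2000 + 3000 + 3000) / (4 × 3000) = 75%;
- lighter: (1000 + 2000 + 2000 + 2000) / (4 × 2000) = 87.5%.

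If only the final dose acted, the shares would be 2/4 = 50% and 3/4 = 75%. The average over visits therefore answers a different question from end versus baseline.

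**The case against.** The strongest reply has four parts.

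- **The plan does name a test of primary interest.** A reader might infer that nothing is ranked at all. The text does not support that. The defect is that the named test has no comparison group and no model.
- **Nothing can be selected for the primary outcome.** This stands. A reader might infer that the glutathione result can be picked, or that random regression cannot be fitted to two draws. Neither holds: no random slope is mentioned anywhere, only the version with a free intercept-slope covariance is unidentified, and the usual models agree on the mean change.
- **The end-versus-baseline remark describes an instrument.** It is not a formally assigned third analysis. It concerns the ABC, extends to the SRS by the stated shared purpose, and does not reach the CGI. This stands, though end versus baseline remains an obvious reading of the post-treatment sentence for any score.
- **This is a pilot whose primary aim is not effectiveness, and the error rates are assumption-driven.** Both points are fair. No alpha is stated, a linear trend is only one reading of random regression, and other assumed structures moved the one-score figure as far as 10.6%. The inflation is modest for a single score. It becomes large only when the open choice of ABC subscale is added.

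**Conclusion.** The concern holds in limited form. Two models are assigned to the same measures without precedence, and the sentence meant to decide between them cannot be carried out in a one-arm trial. The primary glutathione comparison is unaffected when pairs are complete.

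For the ABC, SRS and CGI, best-of-three selection on one score raises the false-positive chance from an assumed 5% to roughly 8% to 10%. For the ABC, a free choice among five subscales raises it to 29% to 42%. These figures assume two-sided 5% tests, complete data and the correlation structures used. The 75% and 87.5% shares hold only under proportionality to dose. That two rules conflict rests on the text alone.

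**What to change.** In Data Analysis:

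1. Delete the SPSS ANOVA sentence and the treatment-main-effect sentence.
2. **Glutathione (primary):** paired end-minus-baseline change, with the mean change and its 95% CI. At n = 24 without dropout, and an assumed two-sided 5%, this has 80% power for a standardised paired change of about 0.60. State what happens to a child with no second draw: carrying the last value forward would carry the baseline and insert a change of zero.
3. **ABC, SRS, CGI:** one mixed model with visit as a categorical factor, fitted to observed data rather than carried-forward values, and one contrast, Week 12 versus Visit 1 before the first dose. Baseline must be named because these scales are also completed at screening. Identify the final visit by week, since the text counts five visits and the visit table has six numbered columns after screening.
4. Name one ABC score; Irritability, for example, matches the hypothesis in Project Goals.
5. Label the time trend, the average over visits and the other subscales as descriptive.

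The cost is a few sentences and no new data. One small downside is that, if an effect appears early, the Week 12 contrast is less precise than the average over visits.
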